Full study protocol and statistical analysis plan

Official Title of the study:

Implementation of a Community-based Resilience Promotion Program to

Only-child Loss Parents in China

Date of the document:

28th October 2017

Contents:

1. Participant Flow

2. Baseline Characteristics

3. Outcome Measures

4. Adverse Event Information

5. Limitations and Caveats

6. Certain Agreements

7. Results Point of Contact

1. Participant Flow

Recruitment Details

We will choose a community in Changsha, where principle investigators' institution located, to recruit the participants. This community has a number of around 260 only-child loss(OCL) parents, and has a social organization to serve the bereaved parents. The recruitment will start at Nov 1st 2017 and last around one week. The recruitment announcement will be distributed to the participants via social worker in their daily online chat group or through telephone call.

Pre-assignment Details [*]

We firstly will assess the recruited people to ensure meeting the inclusion and exclusion criteria. The inclusion criteria are made according to the official documents. OCL Family is one that has given birth to only one child but now has no living birth or adopted child, and the bereaved mother is older than 49 years (medically maximum age for fertility in China).

Those with serious mental disorders or physical illnesses who were not able to complete the intervention and evaluation questionnaire will be excluded.

Than the final enrolled participants can be sure and randomized assignment will be conducted.

Enrollment (total, anticipatory)	150			Record the number of the eligible and the excluded
Allocation (randomized)	Group A	Group B	Group C	Record the number of the received and the unreceived
	50	50	50	
Follow-up (immediately after intervention)				The numbers of each follow-up stages are uncertain by now. But in the latter research, we will record information of the lost and the continued.
Follow-up (3-month after intervention)				
Follow-up (12-month after intervention)				

Arm/Group Information *

There are three groups in the study.

Arm/Group Title *

Positive psychology therapy group= Group A

Resilience promotion therapy group= Group B

Controlled routine activity group= Group C

Arm/Group Description *§

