Positive psychology therapy group will be intervened by a psychotherapy developed from an American psychologist. The positive psychology therapy lasts 8 weeks, and has a group intervention in each week. The themes of each week are start-up, time gift, positive mind, three good things, a thankful heart, life train, active service, end-up.

Resilience promotion therapy group will be intervened by another psychotherapy developed by the researchers. The resilience promotion therapy lasts 8 weeks, and also has a group intervention in each week. The themes of each week are start-up, mutual help, trust in yourself, thanksgiving feedback, care for yourself, emotional management, end-up.

Controlled routine activity group will have routine service delivered by social workers. This group will have routine service delivered by social workers.

Period(s) *

There is only one stage in the study.

Period Title *

Overall Study.

Started *

There will be 150 participants initiating the intervention.

Those 150 participants will be randomly assigned to three groups with around 50 participants in each group.

Completed *

We will do follow-up, and the number in each follow-up will be recorded.

Milestone Title [*]

Before the intervention, we will measure the participants, , and the stage is defined as T0.

We will do follow-up immediately after intervention, 3-month after intervention, 12-month after intervention, defined as T1, T2, T3 respectively.

Reason Not Completed Type [*]

We will record the exact reason (Adverse Event) why participants do not complete the study. The reason may be death, lack of efficacy, lost to follow-up, illness, withdrawal by subject or others.

2. Baseline Characteristics

Arm/Group Information *

Chi-square test will be applied to figure out the difference of enumeration data among three groups. ANOVA will be applied to test the difference of measurement data among three groups. F values and χ^2 values will be displayed to show the baseline data are no different in three groups.

Arm/Group Title *

Positive psychology therapy group

Resilience promotion therapy group

Controlled routine activity group

Arm/Group Description *§

All the recruited participants will be numbered and randomly allocated into three groups by random number table. The grouping results will be announced to the participants according to the random number table.

Overall Number of Baseline Participants *

There will be 150 participants initiating the intervention.

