Baseline Measure Information *

A group of demographic characteristics will be measured in the study, including gender, age, marital status, income per month, gender of lost kid, length of lost kid.

Baseline Measure Title *

- Age * : Continuous(years)
- Gender * : Female, Male
- Marital status: with a spouse, without a spouse
- Income per month: Categorical:
 - <=1000 RMB
 - >1000 and <2000 RMB
 - >=2000 RMB
- Gender of lost kid: Female, Male
- Length of lost kid: Continuous(years)

Measure Type *

- Count of Participants: Gender, Marital status
- Mean: Age, Length of lost kid
- Number: Gender of lost kid, Income per month

Measure of Dispersion *

- Standard Deviation
- Inter-Quartile Range
- Full Range

Baseline Measure Data *

The value(s) for each baseline measure, for each group and overall cannot obtain right now since the study has not been started.

3. Outcome Measures

Outcome Measure Information *

A questionnaire will be used during each measurement, including several scales in it. The saliva test of Dehydroepiandrosterone will also be done in each measurement.

Outcome Measure Type *

- Primary

Outcome Measure Title *

- Psychological resilience: a kind of ability to bounce back from adversity measured by Connor-Davidson Resilience Scale (CD-RISC). It is a self-reported scale by adding up 25 items and the total score ranges from 0-100, with higher score reflects higher resilience. The differences within two times frame are the changes of psychological resilience
- Depression: depressive mood in recent two weeks measured by Zung Self-rated Depression Scale (SDS). It is a self-reported scale by adding up 20 items and the total score ranges from 20-80, with higher score reflects higher depression. The differences within time frames are changes of depression
- Subjective well-being: a feeling of happiness measured by Campbell Index of well-being (IWB). It is a self-reported scale by adding up 8 items and the total score ranges from 2.1-14.7, with higher score reflects higher subjective well-being. The differences within time frames are change of subjective well-being
- Social avoidance: the phenomenon that a person is absent from normal social interaction with others measured by Social Avoidance and Distress Scale(SAD). It is a self-reported scale by adding up 14 items and the total score ranges from 0-14, with higher score reflects social avoidance. The differences within time frames are the changes of social avoidance

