- Sleeping quality: a reflection of one's mood in recent month measured by Pittsburgh sleep quality index(PSQI). It is a self-reported scale, with total score higher than 19 reflects sleeping disorder. The differences within each time frames are the changes of sleeping quality
- Post traumatic growth: the positive growth after an adversity measured by Post Traumatic Growth Inventory(PTGI). It is a self-reported scale by adding up 24 items and the total score ranges from 0-120, with higher score reflects more growth. The differences within time frames are changes of post-traumatic growth
- Health care behavior: a person's self-care behavior measured by Health Promoting Lifestyle Profile-II(HPLP-II). It is a self-reported scale by adding up 40 items in four dimensions. The total score ranges from 40-160, with higher score reflects better health care behavior. The differences within time frames are changes of health care behavior
- Concentration of dehydroepiandrosterone in saliva: a kind of hormone that reflects the person's psychological stress collected by Sarstedt saliva collection tube by chewing the sterile cotton strips for 60 seconds. It will be tested by enzyme-linked immunosorbent assay (ELISA) with Kit Number of HT81012 and Origin site in Canada PLLabs

Outcome Measure unit *

The psychological resilience, depression, subjective well-being, social avoidance, sleeping quality, post traumatic growth, and health care behavior are measured by scales with no unit.

Dehydroepiandrosterone has its concentration unit of pg/ml.

Outcome Measure Time Frame *

There will be four measurements, before the intervention, immediately after intervention, 3-month after intervention, and 12-month after intervention. They are defined as T0, T1, T2, T3 respectively.

Analysis Population Information

Overall Number of Participants Analyzed *

There will be 150 participants totally enrolled in the study.

Outcome Measure Data Table

Measure Type *

- Mean

Measure of Dispersion/Precision *

- Standard Deviation

Outcome Data *

The measurement value(s) for each outcome measure cannot obtain right now since the study has not been started.

Statistical Analysis Overview

Comparison Group Selection [*]

We will compare three groups' data.

Type of Statistical Test [*]

- Superiority
- Other (descriptive analysis)

P-Value [*]

P-Value will be set at 0.05.

Method [*]

- ANOVA
- Chi-Squared
- t-Test, 2-Sided

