- Other: repeated measurement of variance analysis within different measurements among different groups

Estimation Parameter [*]

- Mean Difference (Final Values)

4. Adverse Event Information

Time Frame *§

The intervention lasts 8 weeks, and we will record the adverse event each week. Then we will do follow-up immediately after intervention, 3-month after intervention, and 12-month after intervention. we will record the adverse event at each follow-up.

Adverse Event Reporting Description [*]

We will add relevant information about adverse event after finishing the study.

Collection Approach for Table Default *§

- Systematic Assessment: The psychotherapist will routinely determine whether or not certain adverse events have occurred through regular investigator assessment during intervention and in each follow-up.
- Non-Systematic Assessment: Self-reporting by participants or occasional assessment by the psychotherapist.

Adverse Event Term *

The most possible adverse event may be the psychological discomfort because the participants are experiencing bereavement.

We will provide information for in three tables summarizing adverse events in each group, including all-cause mortality, serious adverse events, and other (not including serious) adverse events.

Organ System *

- Psychiatric Disorders

5. Limitations and Caveats

There may be several limitations.

We may not reach the target number of participants because the bereaved parents present social avoidance and may not interested in the intervention. We will invite social worker to help recruiting and make calls to all registered bereaved parents.

The measurements are mostly based on self-reported scales and may lead to unreliable data. We will give instruction before fulfilling the questionnaire to ensure the participants understood.

6. Certain Agreements

Are all PIs Employees of Sponsor? *

- No: The principal investigator is not an employee of the sponsor

There is no agreement between the agent(university) and the principal investigators. The principal investigators are graduate students in the university. The principal investigators (PIs) can discuss the results of the study at a scientific meeting or any other public or private forum, or to publish in a scientific or academic journal information concerning the results of the study.

7. Results Point of Contact

Name or Official Title *

Professor: [name]

Position title: Director of Nursing Psychology Research Center

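### The plan expects losses to follow-up but states no analysis set, no missing-data rule and no governing method or visit; a mixed model on everyone randomised would settle this cheaply

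*Combined protocol and SAP*

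**What the plan says.** All references are to the combined protocol and SAP.

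- **Losses are expected.** The follow-up rows under Participant Flow state that "The numbers of each follow-up stages are uncertain by now" and that "we will record information of the lost and the continued". On non-completion, the same section says "The reason may be death, lack of efficacy, lost to follow-up, illness, withdrawal by subject or others".
- **Analysis population.** Under Outcome Measures, the entry for the number analysed reads "There will be 150 participants totally enrolled in the study". There is no intention-to-treat, completer or attender definition.
- **Methods.** ANOVA, chi-squared, a two-sided t-test and "repeated measurement of variance analysis within different measurements among different groups" are listed. None is tied to an outcome, a visit or a pair of groups. The significance level is one line: "P-Value will be set at 0.05".
- **Target of estimation.** The estimation parameter is a mean difference in final values, with no visit named. The outcomes are described as changes, for example "The differences within two times frame are the changes of psychological resilience".
- **Visits.** T0 (before), T1 (immediately after), T2 (3 months) and T3 (12 months) are listed without ranking.

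**The concern.** Recording who is lost and why does not say how those people enter the analysis. Three readings are open.

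1. Classical repeated-measures ANOVA uses only people with all four measurements.
2. A t-test or ANOVA at one visit uses everyone seen then, but ignores the earlier scores of those already lost.
3. A claim to analyse all 150 would need imputation or a model, and neither is described.

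These readings can analyse different people and give different estimates. If losses are completely at random, only precision suffers. If they depend on earlier scores, and differently by arm, those who remain are no longer a randomised comparison and the estimate can move either way. Lack of efficacy and illness, both listed as possible reasons, could act like this. Without a rule, the choice of who counts can be made after the data are seen.

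**Working it through.** **The plan's own figure.** 3 × 50 = 150 agrees with the stated enrolment. No effect size, SD, power or dropout rate accompanies it, so there is no sample-size derivation to reproduce.

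**Inputs from the plan.** 50 per arm; three follow-up visits; level 0.05; two-sided (stated for the t-test only).

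**Inputs assumed here.** True difference 0.5 SD; correlation 0.6 between any two visits; baseline always observed; permanent loss of 10% of those remaining at each follow-up visit. Permanent loss is used because most of the listed reasons are departures, not skipped visits.

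**Step 1: who is left.** Share complete = 0.9³ = 0.729. Per arm 50 × 0.729 = 36.45; in total 150 × 0.729 = 109.4.

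**Step 2: power for one pairwise comparison at the last visit.** Two-sample t-test, non-centrality d√(n/2), 2n − 2 degrees of freedom.

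For the likelihood model, the information from each dropout pattern (last seen at T0 10%, at T1 9%, at T2 8.1%, complete 72.9%) is summed and inverted. This gives the variance of the last-visit mean, expressed as an effective n per arm.

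| Analysis | n or effective n per arm | d | Power |
|---|---|---|---|
| No loss, unadjusted | 50 | 0.5 | 70% |
| Completers, unadjusted | 36.45 | 0.5 | 56% |
| Likelihood model, separate baseline means | 41.4 | 0.5 | 61% |
| Completers, adjusted for T0 | 36.45 | 0.5/√(1 − 0.6²) = 0.625 | 75% |
| Likelihood model, common baseline mean | 58.9 | 0.5 | 77% |

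Handling of missing data adds 61 − 56 = 5 points unadjusted and 77 − 75 = 2 points adjusted. Baseline adjustment adds 75 − 56 = 19 points among completers. It is a separate gain and should not be credited to missing-data handling.

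**Step 3: bias when dropout depends on the T1 score.** The effect is 0.5 SD at T1 and T3. The log-odds of missing T3 are logit(0.2), plus or minus 1 per SD of T1 in the affected arm; in the other arm 20% are lost at random. The completer mean at T3 is shifted by 0.6 × (mean T1 of those retained − mean T1 of all).

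Example, low scorers leave the treated arm: the retained T1 mean is 0.648 against 0.500, so the shift is 0.6 × 0.148 = 0.089 and the estimate is 0.589.

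| Who leaves | Missing, treated v control | Completer estimate (true 0.50) |
|---|---|---|
| High scorers, treated only | 32.4% v 20.0% | 0.337 |
| Low scorers, control only | 20.0% v 23.9% | 0.377 |
| Low scorers, treated only | 16.9% v 20.0% | 0.589 |
| High scorers, control only | 20.0% v 23.9% | 0.623 |
| Low scorers, both arms | 16.9% v 23.9% | 0.466 |
| High scorers, both arms | 32.4% v 23.9% | 0.460 |
| At random | 20.0% v 20.0% | 0.500 |

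Only T3 is lost in these scenarios, so a test on everyone seen at T3 has the same bias. A likelihood model that uses T1 returns 0.50 in each row, because dropout depends only on a score it has seen. The one-arm range is 0.39 to 0.58 at correlation 0.4 and 0.28 to 0.66 at correlation 0.8.

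**Step 4: the same mechanism acting on the unseen T3 score.** Same slope and base rate, one arm only, T0 to T2 all observed, by simulation. Completers give about 0.23 to 0.70. The likelihood-type estimate gives about 0.35 to 0.61. The bias is reduced, not removed.

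**The case against.** **The plan never says incomplete cases are dropped.** This is correct. A reader might infer a planned completers-only analysis from the method's name, but the documents do not state the classical form, and ANOVA and a t-test are also listed. What stands is that nothing selects among them, and single-visit tests still lose the earlier scores of those who have left.

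**The entry of 150 may mean that everyone is analysed.** It is worded as an enrolment count. Read the other way, it makes the gap wider, because no method is given for including people with missing visits.

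**The 12-month visit may seem to be the one that governs.** A reader might infer this from the reference to final values. The documents do not support it: no visit is named there and the four measurements are unranked. The last visit is used above only as an example.

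**The gain in power is small.** This is true for the last-visit contrast under permanent loss. For a two-arm group-by-time test with 0.5 SD from T1 onward, the difference is larger: about 83% with no loss, 68% on completers and 77% with a likelihood model. The case still rests mainly on bias and on fixing the rule in advance.

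**A likelihood model does not guarantee an unbiased answer.** This stands. It recovers 0.50 only under missing at random, and it implicitly extrapolates scores beyond death, which is one of the listed reasons.

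**Multiple imputation would also answer the gap.** It would. The mixed model is recommended as the simpler single rule, not as the only valid one.

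**Conclusion.** The gap is confirmed by reading the document: losses are anticipated, and there is no analysis set, missing-data rule, or governing method or visit. Replacing repeated-measures ANOVA as the main analysis is a cheap improvement. It is not the correction of a stated error.

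The size depends wholly on assumed inputs. At the last visit, under permanent loss of 10% per visit and correlation 0.6, missing-data handling is worth about 2 to 5 points of power. The main benefit is less bias: a true 0.50 SD could appear as about 0.34 to 0.62 in completers if dropout depends on T1 in one arm only, as about 0.46 to 0.47 if the same mechanism acts in both arms, and unchanged if losses are random. A reader might infer that the mixed model removes this bias in general. It does so only if data are missing at random.

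**What to change.** Amend the statistical analysis overview as follows.

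- **Main between-group analysis.** Replace repeated-measures ANOVA with a likelihood-based mixed model for repeated measures: group, visit and group-by-visit, unstructured covariance, and T0 as a covariate or a common baseline mean.
- **Analysis set.** Include all randomised participants in the arm assigned, keeping those with partial follow-up.
- **Governing visit.** The sponsor names in advance the visit whose group contrast decides. T3 is one option.
- **Assumption and sensitivity.** State that the model assumes data missing at random, and add an analysis for data not missing at random, for example delta-adjusted.
- **Death.** Say how outcomes after death are treated.
- **Reporting.** Replace the fixed 150 with the numbers contributing by arm and visit.

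The cost is SAP wording and slightly more analysis work, with no new data. The visible downside is that reported numbers per visit will fall below 150.

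### The only stated effect ignores the baseline value, although T0 is collected for all eight primary outcomes; adjusting for it would tighten every comparison at no data cost

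*Combined protocol and SAP*

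**What the plan says.** All references are to section 3 (Outcome Measures) of the combined protocol and SAP, unless stated.

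- **Effect measure.** The Estimation Parameter field has one entry: "Mean Difference (Final Values".
- **Methods.** ANOVA, chi-squared, a two-sided t-test, and "repeated measurement of variance analysis within different measurements among different groups". No covariate, ANCOVA or baseline-adjusted model is described. On significance: "P-Value will be set at 0.05".
- **Schedule.** "There will be four measurements, before the intervention, immediately after intervention, 3-month after intervention, and 12-month after intervention". The plan labels these visits T0 to T3 in that order, so T0 is the baseline.
- **What is measured at T0.** The questionnaire holding the seven scales is given at every measurement. For the eighth outcome: "The saliva test of Dehydroepiandrosterone will also be done in each measurement". All eight outcomes are listed as primary.
- **Change wording.** The seven scale definitions also mention changes; for resilience, "The differences within two times frame are the changes of psychological resilience". The salivary hormone definition has no such sentence.
- **Baseline comparison.** Section 2 plans chi-squared tests and ANOVA to show that the arms do not differ at baseline. No adjustment follows from them.

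**The concern.** A final-value comparison discards what T0 says about each person. Under randomisation and complete follow-up it is unbiased, but its interval is wider than it need be whenever T0 predicts the follow-up value. With about 50 per arm, no sample-size justification, and the plan's own warning in section 5 that recruitment may fall short, precision that needs no further data is worth having.

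T0 is not wholly unused. It is most naturally one level of the planned repeated-measures ANOVA. There it is a repeated response with the arm means left free at T0, which uses it less efficiently than a covariate does. Neither test from that ANOVA is the stated effect: the group-by-time term is a joint test over visits, and the group main effect mixes a T0 difference, zero in expectation, with the three follow-up differences.

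This point makes no claim about type I error. Clustering by therapy group and the use of 0.05 for eight primary outcomes are separate issues.

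**Working it through.** **Inputs from the documents.** 150 randomised, about 50 per arm (section 1); alpha 0.05 and a two-sided t-test (section 3). The plan gives no power, effect size, SD or correlation, so it has no figure of its own to reproduce.

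**Assumed.** Correlation rho between T0 and follow-up of 0.1 to 0.7; effects of 0.3, 0.5 and 0.8 SD; equal variances; linear relation with T0; independent participants; complete follow-up; one pairwise comparison at one visit.

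**Variance relative to final values.** Final 1; change from T0 2(1 − rho); T0-adjusted 1 − rho². The cut from adjustment is rho²: 1, 9, 25 and 49% at rho 0.1, 0.3, 0.5 and 0.7.

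**95% half-widths in SD units, n = 50 per arm.**

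- Final: t(98 df) × √(2/50) = 1.984 × 0.200 = 0.397.
- Adjusted: t(97 df) × √(2(1 − rho²)/50). At rho 0.5: 1.985 × √0.030 = 0.344.
- Estimating the slope multiplies the adjusted variance by about 1 + 1/(2n − 4) = 1 + 1/96 = 1.010.

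| rho | Adjusted | Adjusted, with slope cost | Change from T0 | Equivalent final-value n per arm, 50/(1 − rho²) |
|---|---|---|---|---|
| 0.1 | 0.395 | 0.397 | 0.532 | 50.5 |
| 0.3 | 0.379 | 0.381 | 0.470 | 55 |
| 0.5 | 0.344 | 0.346 | 0.397 | 67 |
| 0.7 | 0.283 | 0.285 | 0.307 | 98 |

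At rho 0, with slope cost, the adjusted half-width is 0.399, which is 0.5% wider than 0.397.

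**Power (two-sided noncentral t).** Adjusted columns exclude the slope cost.

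| Effect | Final | Adjusted, rho 0.1 | 0.3 | 0.5 | 0.7 |
|---|---|---|---|---|---|
| 0.3 SD | 31.8% | 32.0% | 34.4% | 40.3% | 54.8% |
| 0.5 SD | 69.7% | 70.1% | 73.7% | 81.5% | 93.4% |
| 0.8 SD | 97.7% | 97.8% | 98.6% | 99.6% | >99.9% |

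With the slope cost, the 0.5 SD row becomes 73.3, 81.1 and 93.2% at rho 0.3, 0.5 and 0.7. A simulation of three arms of 50 (6000 runs per setting, residual pooled over arms) gave 73.7, 82.4 and 93.2%, with bias of at most 0.005 SD.

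**The repeated-measures ANOVA.** For a constant effect d, the group main effect estimates (0 + d + d + d)/4 = 0.75d. For reference only, compare 1-df analyses of the T1–T3 average, with a constant 0.5 SD effect and all correlations equal to rho:

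| Analysis | Relative variance | Power at rho 0.3 / 0.5 / 0.7 |
|---|---|---|
| Unadjusted average | (1 + 2rho)/3 | 92 / 86 / 79% |
| Average minus T0 | (1 + 2rho)/3 + 1 − 2rho | 73 / 86 / 97% |
| T0-adjusted average | (1 + 2rho)/3 − rho² | 96 / 97 / 99% |

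**Clustering.** Section 1 describes weekly group sessions: "The positive psychology therapy lasts 8 weeks, and has a group intervention in each week". Assume therapy groups of 10 in arms A and B and an ICC of 0.05; neither is in the documents. The design effect is 1 + 9 × 0.05 = 1.45. The variance cut is rho²/1.45 for A v B and 2rho²/(1.45 + 1) for A or B v C: 6/17/34% and 7/20/40% at rho 0.3/0.5/0.7. At ICC 0.10 the design effect is 1.90 and the cuts are 5/13/26% and 6/17/34%.

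**The case against.** The strongest reply is that the comparator above is the plan's weakest use of T0. Seven outcome definitions mention change and a repeated-measures ANOVA is planned, so T0 may be used more than the Estimation Parameter entry suggests. Against a single-visit change score the variance ratio is (1 − rho²)/(2(1 − rho)) = (1 + rho)/2. At rho 0.7 the cut is then 15%, not 49%, and power at 0.5 SD goes from 89.2 to 93.4%, a gain of about 4 points rather than 24. That is correct, but it does not favour change scores: at rho 0.3 they give 55.3% power against 73.7% adjusted. Apart from the small slope cost, adjustment is at least as precise as either alternative, so it spares the choice between them.

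Three further points stand in part:

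- **The benefit rests on an unknown rho.** It may be low for some outcomes or at 12 months, and the plan itself warns of unreliable self-report. At rho 0.3 the gain over final values is only 2 to 4 points of power for 0.3 to 0.5 SD.
- **It is not strictly free.** The slope cost cancels the gain at rho 0.1. The loss at rho 0 is 0.5% of the interval width.
- **It is an efficiency matter, not an error of validity.** Agreed, and it is graded as such.

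It is also fair that a longitudinal model is a larger change than adding one covariate to a single-visit analysis, and that it does not settle the primary visit, multiplicity, a missing T0 value or residual checks. Those are separate gaps that exist under the current wording too.

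**Conclusion.** The point holds. The sole stated effect is an unadjusted final-value difference, no T0 covariate is planned, and T0 is available for every primary outcome. Adjustment narrows the single-visit interval by about 4, 13 or 28% at an assumed rho of 0.3, 0.5 or 0.7, slope cost included. The gain is negligible at low rho, may differ by outcome and visit, and shrinks but remains under the assumed therapy-group clustering. The plan mentions no confidence intervals, so the narrowing applies to whatever interval accompanies the mean difference. The omission is certain from the text; the size of the benefit is conditional on rho. It should be fixed, but nothing in the current estimate is biased because of it.

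**What to change.** Replace the Estimation Parameter entry with wording such as:

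> Baseline-adjusted mean difference between arms at T1, T2 and T3, from a longitudinal model with arm, visit, arm × visit, the T0 value of the same outcome and T0 × visit, with unstructured within-person covariance.

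Use it for all eight outcomes. State that T0 enters as a covariate and not as a repeated outcome, that this model is the treatment comparison, and that changes from T0 are descriptive summaries only. That also removes the ambiguity between final values and the change wording in the scale definitions. Any therapy-group clustering term is decided separately, and this wording does not exclude one.

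The cost is wording in the analysis plan, best settled before outcome data are seen. No extra participants, visits or measurements are needed.

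### The plan describes no weekly contact between Group C and the named adverse-event assessor, so non-serious events in the 8 weeks may be under-recorded there and not comparable by group

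*Combined protocol and SAP*

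**What the plan says.** Section 4 (Adverse Event Information) of the combined protocol and SAP sets the schedule under Time Frame: "The intervention lasts 8 weeks, and we will record the adverse event each week", and then "we will record the adverse event at each follow-up". Neither statement names or excludes an arm.

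Under Collection Approach, the systematic route is: "The psychotherapist will routinely determine whether or not certain adverse events have occurred through regular investigator assessment during intervention", and the same sentence extends this to every follow-up. The non-systematic route is: "Self-reporting by participants or occasional assessment by the psychotherapist". The psychotherapist is the only professional named in either route.

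Under Adverse Event Term, the plan expects psychological discomfort to be the most likely event. It promises "three tables summarizing adverse events in each group", covering all-cause mortality, serious events and other events. It attaches no caveat about how events were found in each arm.

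Section 1, Arm/Group Description, gives Groups A and B a psychotherapy lasting 8 weeks with one group session a week. For the third arm it says: "Controlled routine activity group will have routine service delivered by social workers". No contact schedule is given for Group C, and social workers are given no adverse-event task.

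**The concern.** The plan promises weekly recording but names an assessor who has a described weekly occasion in only two of the three arms. Staff following the document would not know who asks Group C about events during the 8 weeks, how, or when.

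The expected event makes this matter. Psychological discomfort is found largely by asking or observing. Self-report is a weak substitute here, because section 5 itself describes these parents as socially avoidant. If A and B are asked every week and C is not, two errors follow: the therapies look more harmful than routine service, and distress in Group C during the 8 weeks goes unrecorded. The outcome questionnaires do not fill the gap, since none falls between T0 and T1.

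**Working it through.** The plan gives no adverse-event rate and no calculation on this point, so there is no figure to reproduce. The check is a comparison of sections, a count, and two illustrations.

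**1. Sections side by side**

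| Item | Groups A and B | Group C |
|---|---|---|
| Weekly recording promised (section 4, Time Frame) | yes, no arm excluded | yes, no arm excluded |
| Professional assessor (section 4, Collection Approach) | psychotherapist | psychotherapist |
| Described weekly occasion in the 8 weeks (section 1) | group psychotherapy session | none; routine service by social workers |
| Self-report route | open | open |
| Assessment at T1, T2, T3 | yes | yes |

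The arms differ only in the third row, so any imbalance is confined to the 8 weeks.

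**2. Count of scheduled checks**

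- Groups A and B: 8 weekly + 3 follow-ups = 11.
- Group C, if weekly recording reaches it: 8 + 3 = 11.
- Group C, if weekly recording happens only at therapy sessions: 3.

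The documents do not settle which applies to Group C.

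**3. Illustration at the worst case (11 against 3)**

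Assume the same chance p of a recorded event at each check in every arm, with checks independent. The proportion with at least one recorded event after k checks is 1 − (1 − p)^k.

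| Assumed p | A or B, k = 11 | C, k = 3 |
|---|---|---|
| 0.02 | 0.199 | 0.059 |
| 0.05 | 0.431 | 0.143 |
| 0.10 | 0.686 | 0.271 |

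There is no true difference between arms in this table. The values of p are assumptions. The model also treats a weekly check and a follow-up check as equally productive, and supposes that T1 recovers nothing from the preceding 8 weeks in Group C.

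**4. Illustration by detection fraction**

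Assume equal true risk r in both arms and full detection in A (or B). In C only a fraction d is detected, so its recorded risk is r × d. With n = 50 per arm (section 1) and two-sided alpha 0.05 (section 3), the chance that a two-proportion comparison gives p < 0.05 against C is

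Φ{ [r − rd − 1.96 √(2m(1 − m)/n)] / √([r(1 − r) + rd(1 − rd)]/n) }, where m = (r + rd)/2.

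For r = 0.20 and d = 0.50, rd = 0.10 and m = 0.15. The first root is √(2 × 0.15 × 0.85/50) = 0.0714 and the second is √((0.16 + 0.09)/50) = 0.0707. This gives Φ{(0.10 − 0.140)/0.0707} = 0.286.

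| r | d = 0.75 | d = 0.50 | d = 0.25 |
|---|---|---|---|
| 0.10 | 0.064 | 0.155 | 0.339 |
| 0.20 | 0.096 | 0.286 | 0.624 |
| 0.30 | 0.133 | 0.434 | 0.832 |

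At r = 0.20 the expected counts are 10 in A against 7.5, 5 and 2.5 in C. Both r and d are assumed. At d = 1 there is no distortion.

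**The case against.** A reader might infer that the plan itself sets up unequal ascertainment, with 11 checks in A and B, 3 in C, and Group C seen only by social workers. The documents do not support that reading. Weekly recording is promised with no arm excluded, and the systematic route is described as a regular assessment without being tied to therapy sessions. The psychotherapist could assess Group C outside any session. That social workers deliver Group C's service does not say who collects its safety data. The plan does not state who runs the A and B sessions either, so the link between sessions and checks is inferred for those arms too.

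Other points on this side also stand. Self-report is a separate route open to every arm. If T1 asks about the preceding 8 weeks, part of any gap closes. The tables are described as summaries, and no between-arm test of adverse events is specified. Depression and the other scales are measured in all arms at T0 to T3.

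Together these points make the concern conditional but do not remove it. Promising weekly recording in all arms does not supply a means of doing it in Group C. Tables laid out by group will be read across groups whether or not a test is run.

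**Conclusion.** The concern holds in conditional form. The named procedure has a described weekly occasion in two of the three arms whose events are then tabulated together. If the weekly checks happen at therapy sessions, the table of other (non-serious) events over the 8 weeks will be biased towards fewer events in Group C.

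It would be tempting to say that the whole safety comparison is uninterpretable. That goes too far: all-cause mortality depends little on weekly questioning, serious events probably less than non-serious ones, and the T1 to T3 assessments exclude no arm.

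The size cannot be derived from the documents. It runs from nil, if Group C is in fact assessed weekly in the same way, to the 11-against-3 worst case. The intermediate figures rest wholly on assumed event rates and detection fractions. The point is worth correcting in the plan because the bias is plausible, falls on the very event the plan expects, and is cheap to prevent.

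**What to change.** **Preferred.** Use the same short adverse-event checklist, on the same schedule and through the same assessor role, in all three arms during the 8 weeks and at T1, T2 and T3. State who that assessor is for Group C and by what contact. Social workers are one possible role, since Recruitment Details says they reach parents through a chat group and by telephone. Choosing them would mean changing the assessor named in section 4 for every arm. The cost is a checklist and a brief weekly contact in Group C, which slightly alters routine service as the control condition.

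**Fallback.** If a common weekly check is not adopted, compare arms only on events collected in the same way at T1, T2 and T3. Report events noted at the A and B sessions in a separate table, without comparison to Group C, and say why in a footnote. The cost is a split table.
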